### **8.2.1 ADA and efficacy**

Since ADA will not be tested in the placebo group, no statistical comparisons of benralizumab versus placebo by ADA status (positive/negative) are planned. The effects of ADA on the primary and key secondary endpoints calculated through EOT will be evaluated through summary statistics by ADA status (treatment-emergent ADA positive, ADA negative), if enough data are available. However, it could have difficulties to draw solid conclusions due to no comparisons.

### **8.2.2 ADA and safety**

Adverse events and SAEs during the study (separately for on-treatment and on-study periods) will be summarised by ADA status (treatment-emergent ADA positive, ADA negative), if enough data are available. The on-treatment and on-study periods are as defined in Section 3.6.1. AEs and SAEs will also be evaluated by causality as assessed by the investigator. The potential impact of ADA on hypersensitivity will also be assessed.

### **8.2.3 ADA and eosinophil levels**

Eosinophil levels will be summarised by visit for the following ADA response categories of participants: treatment-emergent ADA positive, ADA negative, ADA persistently positive, and ADA positive with titre > median of maximum titre, if enough data are available. A line plot of eosinophil levels by visit and ADA status will also be presented.

### **8.2.4 ADA and PK**

Benralizumab serum concentrations will be summarised by visit and ADA status (treatment emergent ADA positive, ADA negative, ADA persistently positive, ADA positive with titre > median of maximum titre) for participants in the PK analysis set, if enough data are available.

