Post-menopause confirmation (FSH)	X	-	-	-	-	-	-	-	-	-	-	-	-	-	-	-	-	-	Section 8.2.1.1
Hepatitis/HIV screening	X	-	-	-	-	-	-	-	-	-	-	-	-	-	-	-	-	-	Section 8.2.1.2
Pharmacokinetics sample prior to IP administration	-	X	X	-	X	-	X	-	-	X	-	-	X	-	-	-	-	-	Section 8.5.1
Immunogenicity sample (ADA)	-	X	-	-	X	-	X	-	-	X	-	-	X	-	-	-	-	-	Section 8.5.2
CCI																			

Table 2 Schedule of Site Visit Activities

Procedure	Run-in	Double-blind placebo-controlled treatment period						Double-blind extension period						Follow-up		
Visit	1	2	3	4	5	6	7	8	9	10	11	12	13	14	15	16
Week ^a	-4 wk to -10 days ^b	0	4	8	12	16	20	24	28	32	36	40	44	48	52	60
IP administration ^f	-	X	X	X	X	X	X	X	X	X	X	X	X	X	-	-
CC1																
Skin biopsy	-	X	-	-	X	-	-	X	-	-	-	-	-	-	-	Section 8.6
Investigational product administration																
IP administration ^f	-	X	X	X	X	X	X	X	X	X	X	X	X	X	-	-

^a The window for Visits 3 through 16 will be \pm 3 days.

^b The run-in period is a maximum of 4 weeks and minimum of 10 days.

^c Unscheduled Visit: may be initiated as needed; procedures should be performed as clinically indicated at the discretion of the Investigator.

^d Investigational Product Discontinuation: In case of early discontinuation from investigational product, visit procedures should be performed 4 weeks \pm 7 days after the last dose of IP or as soon as feasible if this interval is missed (eg, if decision on discontinuation was made later). Note: The IPD visit replaces the nearest regular visit.

^e It is recommended that vital signs are assessed before any interventional study procedures (blood test collection, IP administration).

^f Review of self-administration of IP procedures may be offered at Visits 2 and 3.

ADA, Anti-drug antibodies; AE, Adverse Event; ECG, Electrocardiogram; EOT, End of treatment; FSH, Follicle-stimulating hormone; HIV, human immunodeficiency virus; IP, Investigational product; IPD, Investigational Product Discontinuation; PRO, Patient-reported outcomes.

All within-window PRO assessments (Table 3) that have not been completed prior to a site visit will be completed at the site before any other study procedures are conducted.

Table 3 Schedule of PRO Assessments

Instruments	Schedule
Daily PRO: UPDD Question 1	Every morning ^a . First assessment at home the day after Visit 1.
Daily PROs: UPDD Questions 2-7	Every evening ^b . First assessment at home on the day of Visit 1.

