#### **2.1.4 Pharmacokinetic analysis set**

All participants who received benralizumab and from whom PK blood samples are assumed not to be affected by factors such as protocol violations (eg, received wrong dose) and who had at least one quantifiable serum PK observation post first dose.

All PK summaries will be based on this analysis set.

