### **3.3.10 Serum benralizumab concentration**

All PK samples will be collected before administration of study medication according in accordance with the visit schedule provided in Tables 1 and 2 of the CSP.

Concentration results below the lower limit of quantification (BLQ) will be set to LLOQ/2 for analysis and will be listed as <LLOQ.

Drug concentration information that would unblind the study will not be reported to investigative sites or blinded personnel until the study has been unblinded.

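### The ADA-by-concentration summary drops participants below quantification at every post-dose sample, so it can understate an effect of ADA on exposure

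*SAP*

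**What the plan says.** SAP 8.2.4 summarises serum concentration by visit and ADA status (treatment-emergent positive, negative, persistently positive, titre above the median of maximum titres) "for participants in the PK analysis set, if enough data are available". SAP 2.1.4 and Protocol 9.3 admit a participant to that set only with "at least one quantifiable serum PK observation post first dose", alongside a condition on samples affected by protocol violations.

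SAP 3.3.10 says that BLQ results "will be set to LLOQ/2 for analysis and will be listed as <LLOQ". A BLQ result therefore has an analysis value and is not discarded.

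The SAP does not agree with itself on the analysis set:
- SAP 2.1.3 places ADA analyses on the safety analysis set.
- SAP 2.1.4 states "All PK summaries will be based on this analysis set", and Protocol 9.3 says the same.
- SAP 4.2.7.10 summarises concentration by visit and treatment on the safety analysis set.
- SAP 8.2 defaults to the safety analysis set unless otherwise specified, and 8.2.4 uses that exception.

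**The concern.** Protocol 9.4.4 and SAP 4.2.7.11 say the impact of ADA on pharmacokinetics will be assessed, and pharmacokinetics and immunogenicity are a stated secondary objective. The comparison in 8.2.4 is of concentration between ADA groups, yet entry to it requires a measurable concentration. A participant with no measurable drug in any post-dose sample may be the clearest case of the effect being studied, and is the one left out. Removing such participants can only raise the summarised concentrations of the group they belong to. If ADA is the cause, that group is the ADA-positive one, and the table moves towards showing no effect. The exclusion also serves no analytical need, because the LLOQ/2 rule already gives these results a value.

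**Working it through.** The documents give no figure to reproduce on this point: no LLOQ, ADA incidence, expected concentration or expected number excluded. The check sets the rules against each other, then illustrates with assumed inputs.

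**Step 1. Who is removed.** Applying SAP 2.1.4 and SAP 3.3.10 together:
- Quantifiable at Week 4 and BLQ at all later visits: stays in; the later visits enter as LLOQ/2.
- BLQ at some visits only: stays in.
- BLQ at every available post-dose sample: removed from every visit.

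**Step 2. How many samples must be BLQ.** In Protocol 1.3 the row "Pharmacokinetics sample prior to IP administration" has six marks, at Weeks 0, 4, 12, 20, 32 and 44 as far as the columns can be read (alignment after Week 12 is uncertain). Week 0 precedes the first dose, leaving 6 − 1 = 5 post-dose samples. A placebo participant who starts benralizumab at Week 24 has two on-drug samples on the same reading (Weeks 32 and 44). An early discontinuer may also have few. If each sample is BLQ independently with probability b, all k are BLQ with probability b^k:

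| b | k = 5 | k = 2 |
|---|---|---|
| 0.5 | 0.03 | 0.25 |
| 0.8 | 0.33 | 0.64 |
| 0.9 | 0.59 | 0.81 |

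Independence is an assumption; positive correlation within a participant would raise these figures. For switchers there is a further condition. Protocol 8.5.1.1 assays concentration only in samples from the benralizumab arm, and SAP 8.2.1 says ADA is not tested in the placebo group. Neither says whether samples taken after the switch are included.

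**Step 3. Geometric mean ratio, ADA-positive to ADA-negative.** Assume that ADA-negative values, and quantifiable ADA-positive values, equal m × LLOQ. A share f of ADA-positive participants is BLQ at the visit, and a share a of all ADA-positive participants is BLQ throughout.
- Everyone kept: ratio = (0.5/m)^f.
- PK set: ratio = (0.5/m)^f′, with f′ = (f − a)/(1 − a).

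With m = 50, 0.5/m = 0.01:

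| f | everyone kept | a = 0 | a = 0.05 | a = 0.10 | a = 0.20 |
|---|---|---|---|---|---|
| 0.2 | 0.40 | 0.40 | 0.48 | 0.60 | 1.00 |
| 0.5 | 0.10 | 0.10 | 0.11 | 0.13 | 0.18 |

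For f = 0.2 and a = 0.10, the pair (everyone kept, PK set) is 0.55 and 0.72 at m = 10, and 0.30 and 0.51 at m = 200.

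**Step 4. Summary statistics in a small group.** Assume 15 treatment-emergent positives, 600 units in all who are quantifiable, LLOQ/2 = 2, and k participants BLQ throughout.
- Mean, everyone kept: ((15 − k) × 600 + 2k)/15 = 560, 520, 480 for k = 1, 2, 3, which is 7%, 13% and 20% below 600.
- Geometric mean, everyone kept: exp(((15 − k) ln 600 + k ln 2)/15) = 410, 280, 192.
- Median, everyone kept: 600 in each case. Minimum: 2.
- PK set: 600 for all four statistics.

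If the above-median titre category held 7 participants and one was BLQ throughout, the mean would be (6 × 600 + 2)/7 = 515 and the geometric mean exp((6 ln 600 + ln 2)/7) = 266, against 600 in the PK set.

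**The case against.** A reader might infer that everyone whose drug was cleared by ADA is removed, and that the effect is therefore understated. The documents do not support either statement. A single quantifiable value retains the participant, and later BLQ visits count as LLOQ/2. A fully sampled participant must be BLQ at all five samples, the first at Week 4, before the first post-baseline ADA sample (Week 12 as read). A reader might also infer that ADA-negative participants are never excluded this way; nothing in the documents establishes that.

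Three further points count against a strong reading. SAP 4.1 lists mean, SD, median, minimum and maximum as the descriptive statistics. The largest drops above are in geometric means, which it does not list, and the median does not move in the 15-participant example. Excluded participants also remain visible elsewhere: in the safety-set concentration summary (SAP 4.2.7.10) and in the listing of ADA-positive participants with titre, concentration and eosinophil level (SAP 8.2). Finally, 8.2.4 is descriptive and produced only if data suffice.

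All of this stands, and it limits the size of the problem. It does not remove it. The Week 4 sample is not full protection: treatment-boosted participants have ADA before the first dose, and with no Week 4 ADA sample a first positive at Week 12 does not show that ADA was absent at Week 4. A listing or a table by treatment arm does not correct a table by ADA status.

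**Conclusion.** The point holds as a conditional risk. SAP 8.2.4 removes participants who are BLQ at every available post-dose sample and, where ADA is the cause, can make exposure in ADA-positive participants look closer to that in ADA-negative ones than it was. The risk is greatest with few on-drug samples (early discontinuers, and placebo participants who switch at Week 24 if their samples are assayed) and in small ADA categories. If nobody is BLQ throughout, this condition changes nothing.

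The size cannot be derived from the documents. The illustrations rest on assumed concentrations, LLOQ, group sizes and BLQ shares, and on unaffected exposure in every quantifiable ADA-positive participant. The issue is minor: it touches a descriptive output for a secondary objective and no primary, key secondary or multiplicity-controlled result. It is worth correcting because the change is cheap and the conflicting set statements need resolving anyway.

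**What to change.** 1. In SAP 8.2.4, use all participants who received benralizumab and have at least one evaluable post-first-dose PK sample, whether quantifiable or BLQ, with BLQ set to LLOQ/2 as in 3.3.10. Keep the existing exclusion of samples affected by dosing errors.
2. In the same table, show by ADA status the number BLQ at each visit and the number BLQ at all samples.
3. Reconcile the set statements in SAP 2.1.3, 2.1.4, 4.2.7.10 and 8.2.4 and in Protocol 9.3, so that each concentration and ADA output has one named set. Editing 8.2.4 alone would leave it in conflict with 2.1.4.
4. State whether post-switch samples from the placebo arm are assayed for concentration and ADA.
5. Record the change in SAP Section 6, since the protocol also assigns all PK summaries to the PK set.

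The cost is a few SAP sentences, one population flag and two sets of counts. The set change and the counts need no new samples or assays.

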### **8.3 Partial dates for adverse events and prior/concomitant medications**

Dates missing the day, or both the day and month of the year will adhere to the following conventions to classify TEAEs and to classify prior/concomitant medications:

- The missing start day will be set to:
  - First day of the month of occurrence, if the start YYYY-MM is after the YYYY-MM of first study treatment
  - The day of the first study treatment, if the start YYYY-MM is the same as YYYY-MM of the first study treatment
  - The date of informed consent, if the onset YYYY-MM is before the YYYY-MM of the first study treatment.
- The missing end day will be set to:
  - The last day of the month of the occurrence, if the end YYYY-MM is after the YYYY-MM of the first study treatment.
  - Death date if the participant died in the same month.
  - The day of last study treatment if the YYYY-MM of occurrence is the same as the last study treatment.
- If the start date is missing both the day and month, the start date will be set to:
  - January 1 of the year of occurrence.
  - The date of the first study treatment, if the start year is the same as the year of the first study treatment
- If the end date is missing both the day and month, the date will be set to:
  - December 31 of the year of occurrence.
  - Date of death if the participant died in the same year
  - Last study treatment date if the year of occurrence is the same as the last study treatment date.
- If the start date is null, the date will be set to:
  - The date of first study treatment.
  - January 1 of the same year as the end date, if the end date suggests that the start date could be prior to the date of first study treatment.
- If the end date is null and not recorded as ongoing, the date will be set to:
  - The date of the first study treatment, if the start date is prior to the date of first study treatment.
  - The date of last visit, if the start date is on or after the date of first study treatment.

If the end date is null and recorded as ongoing, the end date will not be imputed.

SIGNATURE PAGE – WET INK

Protocol	D3259C00001	
Document Name	Statistical Analysis Plan	
Document Version	1.0	
Document Date	16 October 2020	
Wet Ink Signature		
Name	PPD	
Position	Document Author, IQVIA Biostatistician	
Signature Date	16 October 2020	
Signature	PPD	

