### **3.4.1 Adverse Events**

AEs (including SAEs) experienced by the participants will be collected throughout the entire study and will be coded using the latest version of the Medical Dictionary for Regulatory Activities (MedDRA) that will have been released for execution at AstraZeneca/designee per the Data Management Plan.

The following events are considered treatment emergent:

- AEs with an onset date on or after the first dose of IP
- Worsening of pre-existing events on or after first dose of IP

Treatment emergent AE data will be categorized according to their onset date into the following study periods:

- AEs in the pre-treatment period are defined as those with an onset prior to the day of first dose of study treatment.
- AEs in the on-treatment period are defined as those with onset date between day of first dose of study treatment and the day of the scheduled EOT visit or date of last dose + 30 days, whichever is earlier. If the upper limit is after the end of on-study period, then the upper limit is set to the end of on-study period.
- AEs in the on-study period are defined as those with onset on or after the day of first dose of study treatment.
- AEs in the post-treatment period are defined as those with onset date after the on-treatment period defined above.

If an AE has a missing onset date then unless the stop date of the AE indicates otherwise, this will be considered an on-treatment AE. Similarly, if an AE has a partial onset date, then unless the partial onset date or the stop date indicates otherwise, this will be considered an on-treatment AE.

On-treatment AEs in the double-blind period are defined as those with an onset date between the day of first dose of double-blind period treatment and day prior to first dose in extension period, or last dose in double blind period + 30 days for those who do not enter the extension period. On-treatment AEs in the extension period are defined as those with an onset date on or after day of first dose in extension period up to day of EOT visit or last dose + 30 days.

AEs that have missing causality (after data querying) will be assumed to be related to study drug.

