All analyses across the 24-week double-blind period will include 3 treatment groups comprising, respectively, all participants randomised to benraliuzmab 60 mg initial dose (n=60), all participants randomised to benraliuzmab 30 mg initial dose (n=60) and all participants randomised to placebo initial dose (n=40).

For Week 52 analyses, data over the entire 52-week treatment period will be presented in summaries and data listings with the 5 individual treatment groups to initial dose and maintenance regimen. If it is suitable to pool the data across the initial dose groups to enable one comparison of Q4W versus Q8W with 60 participants per arm, then the model will

include 3 treatment groups (those randomised to benralizumab then Q4W maintenance, those randomised to benralizumab then Q8W maintenance and those randomised to placebo followed by benralizumab treatment). If pooling of treatment groups for Q4W versus Q8W dosing is deemed not appropriate, then the model will include the 5 individual treatment groups to initial dose and maintenance regimen.

Key efficacy tables will also summarise data from start of benralizumab, key safety tables will be produced from start of benralizumab to explore changes from starting active study medication.

The data analyses will be conducted using the SAS® System (SAS Institute Inc., Cary, NC). All SAS® programs used to generate analytical results will be developed and validated according to AstraZeneca SAS® programming standards and validation procedures.

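### The AE onset-date rules have no anchor at the Week 24 switch, so in the placebo-to-benralizumab arm some incompletely dated AEs from the start of benralizumab are assigned to the placebo period

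*SAP*

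**What the plan says.** SAP 8.3 states that partial dates "will adhere to the following conventions to classify TEAEs and to classify prior/concomitant medications". Its rules for an incomplete onset date are:

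- Day missing, month later than the month of first study treatment: "First day of the month of occurrence, if the start YYYY-MM is after the YYYY-MM of first study treatment". In the month of first study treatment itself, the day of that treatment is used.
- Day and month missing: "January 1 of the year of occurrence", or, where the years coincide, "The date of the first study treatment, if the start year is the same as the year of the first study treatment".
- Nothing known ("If the start date is null, the date will be set to"): the date of first study treatment, or 1 January of the end-date year if the end date suggests an earlier start.

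SAP 3.4.1 splits on-treatment AEs by onset date. The double-blind period runs to the "day prior to first dose in extension period", and the extension period starts with that dose. Under Protocol 4.1.2 and SAP 1.1.2, the placebo arm (n = 40) receives its first benralizumab at Week 24, which is the first extension dose.

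Several outputs depend on that boundary. SAP 4.1 says that "key safety tables will be produced from start of benralizumab to explore changes from starting active study medication". SAP 4.2.8 adds a few extension-only tables, including one view of former placebo participants restricted to their time on benralizumab. SAP 4.2.8.1 uses on-treatment AEs for the 24-week placebo-controlled tables.

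**The concern.** At Week 0 the authors saw the problem and dealt with it: an onset known only to the month of first dose is moved to the dose day, so it counts as on treatment. The placebo arm has a second start, that of active drug, and no onset rule mentions it. An incomplete date near that boundary falls back to the 1st of the month, 1 January or Week 0, each of which tends to lie before the switch.

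At stake are the descriptive tables meant to show what happens when former placebo participants start benralizumab. The AEs at risk of being left out are concentrated in the first weeks of active treatment, which those tables exist to describe.

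**Working it through.** The plan gives no count or rate of partial AE dates, so there is no figure of its own to reproduce. The check applies the rules literally.

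**Inputs.** Onset rules from SAP 8.3; period boundary from SAP 3.4.1; switch at Week 24 = 24 × 7 = 168 days after first dose (Protocol 4.1.2). Assumption: first-dose dates spread evenly over four calendar years (1,461 dates). An AE is misassigned if its true onset is on or after the switch and its imputed onset is before it.

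**Worked cases.**

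- First dose 29 January 2020, switch 15 July 2020. An AE on 20 July with the day missing is set to 1 July: placebo period. With only the year known it is set to 29 January, which is Week 0. An August AE with the day missing is set to 1 August and stays correctly in the benralizumab period.
- First dose 15 September 2020, switch 2 March 2021. An AE on 7 March with the day missing is set to 1 March: placebo period. With only the year known it is set to 1 January 2021: also placebo period.

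**Day missing, onset in the switch month on or after the switch.** By hand, for a 30-day month with a uniform switch day d, the post-switch days total the sum of (31 − d) = 465. Only a switch on the 1st (30 of those days) is classified correctly, so the misassigned share is 1 − 30/465 = 93.5%. The run over real calendars gives 93.6%.

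**Share of true post-switch onsets dated into the placebo period:**

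| Days since switch | Day missing | Day and month missing |
|---|---|---|
| 0–6 | 86.9% | 98.9% |
| 0–27 | 52.4% | 96.0% |
| 0–83 | 17.5% | 88.4% |
| 0–195 (Weeks 24–52) | 7.5% | 73.0% |

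With the month known, the problem is confined to the switch month, so its share falls quickly with time. With only the year known it persists, and is avoided only when the onset year is later than the switch year. A fully missing date goes to Week 0 by default.

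**Direction within this arm.** Of 243,987 simulated true placebo-period onsets, none moved to benralizumab under either the day-missing or the year-only rule. The error runs one way.

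**Weight of one event.** One participant is 1/40 = 2.5 percentage points of the arm. If the sample-size dropout of 10% also held at Week 24 (an assumption), 40 × 0.9 = 36 enter the extension, and one participant is 1/36 = 2.8 points. Either applies only if that participant has no other AE in the same row of the table.

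**The case against.** **The rules do not say they assign a period.** SAP 8.3 says that its dates classify TEAEs and medications, and SAP 3.4 says that no safety data are imputed. Using the dates to split on-treatment AEs is therefore partly an inference. But SAP 3.4 itself points to Appendix 8.3 for partial AE dates, and no other rule is offered. SAP 3.4.1 has its own default for partial onset dates, but that only makes the AE on-treatment. Both periods are on-treatment, so it does not choose between them. SAP section 6 adds nothing.

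**Other anchors exist.** This is correct for end dates, for example "The day of last study treatment if the YYYY-MM of occurrence is the same as the last study treatment". End dates do not set the onset period.

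**A reader might infer that these AEs are lost, or that the placebo-controlled comparison is tilted towards benralizumab.** The documents support neither. The AEs remain in the whole-study tables by five randomised sequences (SAP 4.2.8) and in the AE listing (SAP 4.2.8.1). The same onset rules also apply to the benralizumab arms (planned n = 120), where early-extension AEs are likewise dated back into the 24-week columns. Every column can gain events, and nothing in the plan shows which gains more.

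**Few events.** AEs are asked about at each four-weekly visit with reference to the previous one (Protocol 8.3.4), and visit procedures should precede dosing (Protocol 6.1.1). That should keep incomplete dates rare and helps site queries. It stands as an argument about size. The derivation rule as written does not use the reporting visit.

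**Conclusion.** The gap is real and narrow. In the placebo-to-benralizumab arm, an AE that began after the switch is dated into the placebo period when only its month is known and that is the switch month, unless the switch was on the 1st. The same usually happens when only the year is known or the date is fully missing. These AEs drop out of the extension-period and from-start-of-benralizumab safety tables. Within this arm the error always takes events away from benralizumab.

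The percentages rest on evenly spread first-dose dates and a switch at exactly day 168. They describe what happens to an AE once its date is incomplete, not how many such AEs there will be. That number is not given and is probably small. Safety is descriptive, so no test or efficacy conclusion changes. The priority is low, but the rule gives a wrong assignment that is cheap to correct.

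**What to change.** Add to SAP 8.3, for the placebo-to-benralizumab arm only, and only for the extension-period and from-start-of-benralizumab tables: an incomplete or missing AE onset date is set to the date of the first benralizumab dose when the known parts of the date are compatible with onset on or after that dose and the stop date does not rule it out. State that for those tables this overrides the first-of-month, 1 January and first-study-treatment rules; otherwise it would conflict with the year-only rule whenever one year contains both the first dose and the switch. List the affected events.

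Leave the 24-week controlled tables and the benralizumab arms under the existing rule. Applied to everyone entering the extension, the change would move AEs that truly began on benralizumab in Weeks 0–24 out of the controlled tables.

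The cost is one SAP paragraph, one derivation and one listing. A few AEs that truly began on placebo will be counted under benralizumab in these descriptive tables, which is the conservative direction. Some AEs may appear both in the 24-week placebo column and in the from-start tables, so a footnote should say so. This is a date derivation and does not touch clinical management.

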### **3.1.4 Prior/concomitant medications**

Medications will be categorized according to the WHO Drug Reference List dictionary which employs the Anatomical Therapeutic Chemical (ATC) classification system.

A medication will be regarded as prior if it was stopped on or before the date of randomisation (medication stop date  $\leq$  date of randomisation).

A medication will be regarded as ‘concomitant’ if the start date is on or after the date of randomisation or if it started prior to the date of randomisation and was ongoing after the date of randomisation. If a medication was started and stopped on the date of randomisation, it will be considered as concomitant.

No medication data will be imputed. The handling of partial/missing dates for AEs and prior/concomitant medications is detailed in [Appendix 8.3](#). Duration of AEs and prior/concomitant medications will not be calculated using imputed dates and will instead be set to missing.

Throughout the study, participants will be required to maintain stable doses of their pre-randomisation H1 antihistamine treatment (CSP Section 6.5.1). Participants will be permitted to use additional doses (up to 4 x recommended dose per day) of the pre-randomization H1 antihistamine on days on which symptoms become intolerable, and use should be documented in the ePRO device. A switch of the rescue medication for an individual participant is not permitted (CSP Section 6.5.3).

The number of tablets of rescue medication taken is recorded in the handheld ePRO device as part of the daily Urticaria Patient Daily Diary (UPDD):

- During the past 24 hours, how many tablets of rescue medication did you use in order to control symptoms of your skin condition such as itch or hives?

The weekly number of days of taking rescue medication is calculated by summing the daily use of rescue medication (taken) over the past 7 days. The weekly average amount of anti-histamine medication (including background and rescue) is calculated by summing the recorded multiple of licensed dose taken each day over the past 7 days, and dividing by 7 days. Participants who took no rescue medication and only their daily background medication as per protocol would be presented as 1 time the licensed dose of anti-histamine medication.

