#### **4.2.3 Prior and concomitant medications**

The frequency and percentage of participants reporting usage of prior medications, those reporting use of allowed concomitant medications, and those reporting usage of disallowed concomitant medications (refer to Section 6.5 of the CSP) will be summarised by treatment group and overall. Background medications (e.g. type of antihistamine) will be summarised by treatment group and overall.

The summary tables will present data by generic term within ATC code.

The frequency and percentage of participants reporting usage of rescue medication (taken, not taken) over the past 7 days will be summarised by treatment group and overall for scheduled visits. The frequency and percentage of recorded multiple of licensed dose of antihistamine taken each day over the past 7 days will be summarised by treatment group and overall for scheduled visits.

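### A medication started before first dose with a wholly missing end date and no ongoing flag is normally classed as prior only, which leans towards undercounting concomitant and disallowed use

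*SAP*

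**What the plan says.** SAP 8.3 gives rules for incomplete dates, described as "conventions to classify TEAEs and to classify prior/concomitant medications". Four of its end-date rules matter here:

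- Wholly missing, not flagged as ongoing: "If the end date is null and not recorded as ongoing, the date will be set to" one of two values. For an earlier start it is "The date of the first study treatment, if the start date is prior to the date of first study treatment". For a later start it is "The date of last visit, if the start date is on or after the date of first study treatment".
- Wholly missing, flagged as ongoing: "If the end date is null and recorded as ongoing, the end date will not be imputed".
- Only the year known: 31 December of that year, replaced by the death date or the last treatment date when either falls in that year.
- Only the day missing: rules exist for an end month later than the first-dose month, for the month of death and for the month of last treatment. There is no general rule for an end month equal to the first-dose month.

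SAP 3.1.4 supplies the classes: "A medication will be regarded as prior if it was stopped on or before the date of randomisation". A medication that began earlier is concomitant only "if it started prior to the date of randomisation and was ongoing after the date of randomisation". One that both starts and stops on the randomisation date counts as concomitant.

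SAP 4.2.3 then tabulates, by treatment group, prior medications, allowed concomitant medications and "those reporting usage of disallowed concomitant medications".

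**The concern.** When nothing is known about when a medication stopped, the plan does not leave the question open or take the cautious side. It assigns a stop date that, on the planned schedule, is the latest date that still counts as prior. A participant who started an agent restricted on study before Visit 2, and whose end date was never completed, is therefore left out of the disallowed-concomitant count. The error can run only one way, towards fewer concomitant and disallowed uses.

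The records are plausible. Protocol 6.5 collects all medications from the 3 months before Visit 1, and prior biologics whenever they were given. Inclusion criteria 4 and 6 (Protocol 5.1) admit people who have been on leukotriene receptor antagonists or H2 blockers but ask for H1 antihistamine monotherapy from Visit 1. Stop dates for CSU drugs used before the study therefore matter here.

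**Working it through.** No power or alpha figure bears on this point. The check sets the date rules against the class definitions.

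**Inputs**

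1. Randomisation is study Day 1 (SAP 3.1.3) and takes place at Visit 2 (Protocol 4.1).
2. First dose is at Visit 2, Week 0 (Protocol 4.1.2). On schedule, first dose is therefore also Day 1.
3. Null end date, not ongoing: stop = first-dose date if start < first dose, otherwise stop = last visit (SAP 8.3).
4. Prior if stop ≤ randomisation. For an earlier start, concomitant if still in use after randomisation (SAP 3.1.4).

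**Result for a null end date**

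As an illustration, last visit is put at Week 52: 52 × 7 + 1 = Day 365.

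| First dose | Start | Flagged ongoing | Stop used | Class |
|---|---|---|---|---|
| Day 1 | Day −30 or Day 0 | No | Day 1 | Prior only |
| Day 1 | Day −30 or Day 0 | Yes | none | Concomitant |
| Day 1 | Day 1 or later | No | Day 365 | Concomitant |
| Day 2 | Day −30 or Day 0 | No | Day 2 | Concomitant |
| Day 4 | Day −30 or Day 0 | No | Day 4 | Concomitant |

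In the first row the stop is Day 1 ≤ Day 1, so the record is prior. It is not in use after Day 1, so it is not concomitant. The same-day exception does not help, because it needs the start on Day 1 as well. Moving first dose from Day 1 to Day 2 reverses the class although nothing about the medication has changed.

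**Comparison within SAP 8.3**

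Take the same early start, but suppose the end year is known and equals the year of first dose.

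- If the last treatment falls in that year, the stop is the last treatment date. That is after randomisation for anyone given a dose at a later visit, so the record is concomitant.
- If the last treatment falls in a later year, the stop is 31 December of the first-dose year. That is after randomisation unless randomisation was on that day, so the record is again concomitant.

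Knowing the year normally gives concomitant and knowing nothing gives prior, so less information leads to the less cautious class.

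**Effect of a concomitant default**

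Treating null, not-ongoing end dates as running past randomisation changes the first row of the table to concomitant. Every other combination keeps its class.

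**The case against.** Several points on the other side stand.

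- **Concealment.** A reader might infer that disallowed use is hidden. It is not. The record still appears in the prior-medication summary; what is lost is its place in the concomitant and disallowed tables.
- **Sensitivity analyses.** A reader might infer that the restricted-medication analyses in SAP 4.2.6.3 and the composite responder analysis in 4.2.7.2 will miss these participants. The documents do not support that. Neither section says that it uses the prior/concomitant flag or the imputed dates, and both analyses are optional. The same holds for the prohibited-medication category of important protocol deviations in SAP 2.2.1.
- **Main result.** The primary and key secondary analyses follow a treatment-policy strategy and keep data after changes in background therapy (SAP 4.1). Rescue use comes from the daily diary, not from these dates.
- **Universality.** It would be wrong to say that such a record can never be concomitant. It is concomitant whenever first dose falls after the randomisation date.
- **Corticosteroids.** These are a weak example. Exclusion criterion 10 (Protocol 5.2) already bars use within 4 weeks or 5 half-lives before consent, whichever is longer.
- **Start-date rules.** These do not uniformly favour on-treatment status. Some unknown starts go to consent or to 1 January, so a simple contrast between start and end rules would be selective.
- **A blanket reversal.** Because prior biologics are collected regardless of time, an unconditional concomitant default could label a course given long ago as disallowed use on study.

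None of this supplies a passage that overrides the rule. The sentence in SAP 3.1.4 that medication data are not imputed is followed at once by a reference to 8.3 for missing dates, so it does not do so.

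**Conclusion.** The point holds in a narrow form. It needs four conditions: the end date is wholly null, the record is not flagged as ongoing, the start precedes first dose, and first dose is on the randomisation date. The last is the planned schedule. Under them the record is prior only and is omitted from the concomitant and disallowed-concomitant summaries of SAP 4.2.3. The direction is towards undercounting, and the rule is inconsistent with its neighbours in 8.3.

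The number of such records cannot be obtained from the documents. It is probably small, because concomitant medications are reviewed at each visit. The primary analysis does not change. Any effect on the optional restricted-medication analyses is conditional on their using this flag. This is a minor improvement to a descriptive convention, not a threat to the trial's conclusions.

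**What to change.** In SAP 8.3, leave a null, not-ongoing end date unimputed. Class the medication as concomitant unless other recorded data show that it stopped no later than randomisation, for example the eligibility washout checks for prior biologics or the medication history. Apply the same default when only the end day is missing and the end month is the month of first dose. Add a matching line to SAP 3.1.4, whose definitions do not otherwise place a medication with no stop date and no ongoing flag. State there also whether the analyses in 4.2.6.3 and 4.2.7.2 use this classification.

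The cost is a short text edit in two sections. Concomitant counts will be slightly higher, and a few medications that had in fact stopped may be counted as concomitant. Records that reach the disallowed table only through this default should therefore be identified in the listing, so that they can be told apart from documented use on study.
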